We will stratify based on education level to be largely representative of the UK population (14, 15). We will recruit (approximately):

- 50% NQF 4 Level 4 or above (University degree or equivalent) and 50% NQF Level 3 or below (no University degree)

We will also aim to fulfil the following quotas for age and gender, based on the composition of the UK population (16, 17):

- 50% 18 – 39 and 50% 40 and over
- 50% female and 50% male

We will only recruit up to 10% of the sample as current University students. Students have a high SEP in terms of education, but typically have low disposable income, which may impact relative health motives. This could distort the results if students are recruited in high numbers.

Inclusion and exclusion criteria

Participants are eligible to take part if they:

- Are a UK resident
- Are aged 18 years and above
- Are fluent in English
- Eat an out-of-home meal at least once a month on average
- Have no dietary allergies
- Are not vegan

There are no additional exclusion criteria as this is a real-world study.

Methods

Procedure

Participants will be asked to attend one session at a restaurant from Monday – Saturday between 12 – 5pm. All participants will be asked to verbally consent to taking part in the study, and will be given the opportunity to ask questions before the study begins.

Participants will be asked to order lunch from a menu. The menu will either feature nutrient warning labels next to the relevant menu items (experimental condition), or no labels (control condition). A researcher will ask participants to write their order down on an order form, communicate the order with the kitchen, photograph the meal when it is ready to be served, and photograph the plate when the participant is finished with the meal in order to estimate amount consumed.

After finishing their meal, participants will be asked to fill out an online questionnaire (on an iPad) about their sociodemographic characteristics, health motives, label awareness, salt awareness, perceived message effectiveness, perceived knowledge gain, perceived influence, and support for the introduction of a restaurant salt warning label policy in the UK. The questionnaire will also ask (i) whether any food or drink items were shared with other participants, and, if so, what item(s) were shared and (ii) whether they added any condiments to their meal (see Appendix E).

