If [yes], how would the salt label have influenced your choice? Response options: I would have avoided choosing a meal high in salt; I would have chosen a meal high in salt; Other (free text response)

Policy support

If the UK Government introduced policy requiring restaurant menu items high in salt to feature these labels, how would you feel?" Likert scale ranging from 1 – 5 anchored by "strongly oppose" and "strongly support".

Control: Same as above

Additional thoughts on label

"Please use this box to add any additional thoughts which you may have about the salt label" (open text response).

Control: Same as above

Secondary outcomes

Total salt purchased

Determined based on the total order of the participant, including food and drink. Prior to study commencement, all menu items will be sent for nutritional analysis to determine salt content/100g. Menu items will be weighed before being sent for analysis using kitchen scales (Vitafit VT706), so that specific salt content per serving can be calculated.

Labelled item selected

Determined based on whether the food item selected featured a high in salt warning label (yes = 1, no = 0).

Total salt consumed

Salt consumption will be determined from the order that the researcher takes and an estimation of the proportion of the meal that was consumed. The researcher will take a photograph before and after consumption and will estimate the percentage consumed component(s) of the meal, taking into account whether participants leave a proportion of all meal components or specific components (e.g., low salt or high salt components). Participants will also be asked whether they shared any of their meal with someone else. A random 10% selection of percentage estimates will be performed by a second researcher to measure reliability. Food consumption will then be calculated by subtracting an estimation of the proportion of the meal that was consumed (taking into account if any has been shared) from the food purchase.

Later salt intake

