Information sheet and informed consent	
 - Eligible participants will be e-mailed an information sheet (Appendix B) and consent form (Appendix C). Participants can ask any questions about the study via e-mail. - The researcher will schedule a study visit day, leaving 30-minute gaps between participant groups. Participants may bring a maximum of nine guests aged 18 years or older to the restaurant. - As the guests did not yet receive an online information sheet and consent form, all participants will also be provided with information by the researcher and provide verbal consent. The researcher will answer any questions prior to the study. 				
Meal choice task	
 - Participants will be invited to visit the restaurant. They will be assigned in advance to either the control or experimental condition. Any guests will be in the same condition as the primary participant (i.e., participants will be randomised by table). They will also be given a participant number which they will be required to enter in any questionnaire they complete. 				
	
  
 Control condition	Experimental condition	
   
  
 - Participants will receive a standard menu without nutrient warning labels. 	 
 - Participants will receive a menu featuring a nutrient warning label next to items high in salt. Text at the bottom of the menu will read “[label image] indicates that the salt content of this item is higher than 50% of the daily recommended limit (6g per day). High salt 	
  
	Control condition	Experimental condition	
 - Participants will receive a standard menu without nutrient warning labels. 	
 - Participants will receive a menu featuring a nutrient warning label next to items high in salt. Text at the bottom of the menu will read “[label image] indicates that the salt content of this item is higher than 50% of the daily recommended limit (6g per day). High salt
Control condition	Experimental condition				

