
 - Participants will receive a standard menu without nutrient warning labels. 	
 - Participants will receive a menu featuring a nutrient warning label next to items high in salt. Text at the bottom of the menu will read “[label image] indicates that the salt content of this item is higher than 50% of the daily recommended limit (6g per day). High salt 				

		intake can increase blood pressure and risk of heart disease and stroke.”
	
 - The participants will be asked to order lunch from the menu and a drink (optional) and write this down on an order form (Appendix D) - A researcher will communicate the order with the kitchen, take a photo of the meal when it is ready to be served and take a second photo when the participant is finished with the meal. The researcher will send themselves each photo on WhatsApp labelled with the participant ID. 	
Post-meal assessments (Qualtrics) (Appendix E)	
 - After finishing their meal, participants will be provided with an iPad. They will answer a question about what they think the aim of the study was in an open-ended response format. - Next, participants will complete measures of PME, label awareness, salt awareness, perceived knowledge gain, perceived influence, and policy support. - Finally, participants will answer questions on demographic characteristics (including frequency of eating OOH) and health motives. 	
Later intake	
 - After the restaurant visit (same day), participants will receive a link to an online questionnaire assessing their dietary intake for the rest of the day after the restaurant visit, to be completed before they go to bed (Intake24). - This will enable us to calculate salt consumed post intervention for the rest of that day. - They will also be requested to answer some additional questions on demographic characteristics. 	
Additional demographic questions (Appendix F) and debriefing (Appendix G) (Qualtrics)	
 - After completing the dietary intake questionnaire, participants will be asked to answer some additional questions on demographic characteristics. - Upon completion, participants will be debriefed on study aims. 	

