Reimbursement	
 - Participants will receive £25 which will likely cover their lunch costs and serve as an incentive for people from different SEP strata to participate. Participants will either (i) pay for their own meal at the restaurant and receive £25 via invoice or (ii) have their meal paid for by a researcher using a prepaid card; if this costs less than £25, they can request to receive the remaining amount via invoice, if this costs more than £25, they will need to pay the difference at the restaurant. 	

Statistical analysis

Participant characteristics

Participant characteristics will be presented overall and by experimental condition in a table. Data will include age, gender, ethnicity, highest educational qualification, employment status, BMI, frequency of eating OOH, and hunger. Continuous variables will be summarised as means and standard deviations, and categorical variables will be summarised as counts and percentages.

Measured variables

Primary

A linear regression will be used to assess differences between menu conditions in terms of PME. The between-subjects predictor will be label condition, and the dependent variable will be PME.

Highest education level (categorical: NQF level 4 or above, NQF level 3 or below) will be included as a covariate in the model to account for stratification (30). Health motives (continuous) will be included as a covariate as this may predict outcomes (e.g., health motivated individuals may be more likely to believe a menu with labels will change their behaviour) (30). Age and gender will also be included as covariates as previous work suggests that this can influence ratings of label PME and salt intake (13).

Descriptive analysis will be used to report (overall and by condition) participants' label awareness, salt awareness, perceived knowledge gain, perceived influence, and policy support (dichotomised into support/oppose). Logistic regressions will be performed to assess the odds of (i) being aware of the label, and (ii) being aware of the salt content of the meals in the labelled menu group, using the control menu group as the reference category. The same covariates as above will be included.

Secondary

Linear regressions will be performed to assess differences in menu conditions in terms of total salt purchase and total salt intake. The same covariates as above will be included.

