Appendix E – Post-exposure assessments

Please enter your participant ID. If you are unsure what this is, please ask the researcher.

Please select the letter which is circled on your sticker label. If you are unsure, please ask the researcher.

A (1)

B (2)

End of Block: Default Question Block

Start of Block: Aim guessing

What do you think was the aim of this study?

End of Block: Aim guessing

Start of Block: Food sharing

Did you share any of the food or drink items?

Yes (1)

No (2)

Display This Question:

If Did you share any of the food or drink items? = Yes

What items were shared? Please also give an estimation in % of how much of each item was shared.

Did you add any condiments (e.g., sauce, salt) to your food?

- Yes (1)
- No (2)

Display This Question:

If Did you add any condiments (e.g., sauce, salt) to your food? = Yes

What condiments did you add? Please also give an estimation in teaspoons of how much of each condiment was added.

End of Block: Food sharing

Start of Block: PME

Please consider the following statements in relation to the menu you ordered from.

Not at all (1) A little bit (2) Somewhat (3) Quite a bit (4) A great deal (5)

The menu made me concerned about the health effects of consuming items high in salt. (1)

The menu
made
consuming
items high in
salt seem
unpleasant. (2)

The menu
discouraged
me from
wanting to
consume
items high in
salt. (3)

 End of Block: PME**Start of Block: Attention check**

This question is an attention check, so please answer truthfully. How many times have you visited the planet Mars?

- Several times (1)
- Just once (2)
- Never (3)

End of Block: Attention check**Start of Block: Awareness**

Did you notice any warning labels next to any of the menu items when making your meal selection?

- Yes (1)
- No (2)

Display This Question:

If Did you notice any warning labels next to any of the menu items when making your meal selection?

= Yes

What did the label tell you about?

Healthy items (1)

Organic (2)

Calcium (3)

Sustainable (4)

Added sugars (5)

Vegetarian (6)

Unhealthy items (7)

Salt (8)

Fibre (9)

Gluten free (10)

None of these (11)

Not sure (12)

Display This Question:

If Did you notice any warning labels next to any of the menu items when making your meal selection?

= Yes

Please describe what the warning label said.

Page Break

Did you think about the salt content of the meals when making your selection?

Yes (1)

No (2)

End of Block: Awareness

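### Total salt consumed rests on a visual estimate by the researcher who photographs the meal and can very probably see the menu condition, and no masking of that estimate is stated

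*Combined protocol and SAP*

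**What the plan says.** Measures, Secondary outcomes, Total salt consumed, defines the outcome: "Salt consumption will be determined from the order that the researcher takes and an estimation of the proportion of the meal that was consumed". On who makes the estimate it says: "The researcher will take a photograph before and after consumption and will estimate the percentage consumed component(s) of the meal". The rater is to consider whether particular components, including high-salt or low-salt ones, were left. No weighing of leftovers is described. The check on the estimates is: "A random 10% selection of percentage estimates will be performed by a second researcher to measure reliability".

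The Procedure section describes the role at the table: "A researcher will ask participants to write their order down on an order form, communicate the order with the kitchen, photograph the meal", and then the finished plate. In Study flow, Meal choice task, tables are allocated before the visit ("They will be assigned in advance to either the control or experimental condition"), with guests in the same condition as the primary participant. The same row covers the images: "The researcher will send themselves each photo on WhatsApp labelled with the participant ID".

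Figures 3 and 4 show menus that differ visibly, one with salt labels and a footnote and one without. Appendix E instructs participants: "Please select the letter which is circled on your sticker label. If you are unsure, please ask the researcher". The options are A and B, which correspond to the two menus.

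Statistical analysis, Secondary, then uses the outcome: "Linear regressions will be performed to assess differences in menu conditions in terms of total salt purchase and total salt intake". Under Multiple comparisons, secondary outcomes are tested at alpha 0.05.

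**The concern.** The percentage eaten is the main subjective input to total salt consumed. The rest is an order form and laboratory salt values. A rater who knows the condition and expects diners with the labelled menu to leave more of the salty components can lower the estimates in that arm without meaning to. The rating instruction directs attention to the dimension on which the label is expected to act.

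The 10% second rating does not deal with this. It measures agreement, and two raters who both know the condition and share an expectation can agree well while both are biased. The plan does not say that the second rater is masked, or that agreement will be compared by arm.

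At stake is one secondary comparison. It still matters for two reasons. The Background presents the study as a pilot for effects on food choice and salt intake. The Sample size section also cites an earlier trial of sodium labels with d = 0.03 for salt in grams, while noting important methodological differences. Against an effect of that order, a small rating bias would not be negligible.

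**Working it through.** **Who can see the condition.** The protocol has one role take part in ordering, deal with the kitchen, photograph the plate and estimate the percentage eaten. The menus differ on sight, a whole table shares one condition, and participants unsure of their A/B letter are sent to the researcher. Awareness of condition is the natural reading, but no sentence states it. No section states masking of the estimate.

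**The plan's own figure.** The Sample size section gives 260 participants (130 per condition) for d = 0.35, 80% power, two-tailed, and names salt intake among the outcomes covered.
- Normal approximation: n per arm = 2(1.960 + 0.842)² / 0.35² = 128.1, so 129 per arm and 258 in total.
- Exact t-test: 129.1, so 130 per arm and 260 in total. Power at 130 per arm is 0.803.

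The figure reproduces, and masked rating would leave it unchanged.

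**Illustration of a rating shift.** The documents give no mean or SD for salt intake, so these inputs are assumptions: mean salt per order M = 2.5 to 4 g; SD = 1 to 2 g; a shift of b percentage points on every plate in one arm; no true effect; 130 per arm; diners treated as independent; no covariates.
- Spurious d = (b/100) × M / SD.
- Standard error of d ≈ √(2/130) = 0.124.
- Chance of p < 0.05 = 1 − Φ(1.96 − d/0.124) + Φ(−1.96 − d/0.124).

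| Shift b | M (g) | SD (g) | d | Chance of p < 0.05 |
|---|---|---|---|---|
| 5 | 2.5 | 2 | 0.0625 | 8% |
| 5 | 3 | 1.5 | 0.10 | 13% |
| 5 | 4 | 1 | 0.20 | 36% |
| 2 | 3 | 2 | 0.03 | 6% |
| 2 | 3 | 1 | 0.06 | 8% |

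A 5-point shift therefore gives d of about 0.06 to 0.20 over the assumed range, and a 2-point shift at 3 g gives about 0.03 to 0.06, against a nominal 5% error rate. A cleared plate leaves little room for judgement. If half the plates were cleared, a 5-point shift on the others would average 2.5 points, and the middle row would fall to d = 0.025 × 3 / 1.5 = 0.05.

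**Reach of the second rating.** If the 10% is drawn by participant, 0.10 × 260 = 26 participants have a second rating and 260 − 26 = 234 have one rating only.

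**Outcomes not exposed.** PME is self-reported. Salt purchased and labelled-item selection come from the order. The interim decision uses PME and the odds of selecting a high-salt meal, not intake.

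**The case against.** The strongest reply is that the protocol never says the rater knows the condition. The timing of the rating is not given, and photographing the finished plate so that intake can be estimated fits rating from images later on. The plan speaks of several researchers, so the researcher need not be one person throughout. This stands as a limit on the wording: a reader might infer that intake is documented as rated unmasked, but the documents support only that awareness is very probable and masking is not stated.

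Two further inferences are tempting. One is that the photographs carry nothing but a participant ID and show only the plate. The protocol says they are labelled with the ID; it does not exclude a condition code in the ID, or a menu or sticker in the frame. The other is that masked rating needs no extra staff effort. The number of researchers, their attendance at tables and their capacity to rate more than 10% of meals are not given.

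The plan also has real safeguards: paired photographs, estimates by component, a random second rating and laboratory salt values. The images would allow a masked audit later. These limit random error and make bias checkable, but none of them prevents it.

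**Conclusion.** The concern holds as a modest, avoidable weakness in one secondary outcome. A subjective between-arm measure is assigned to the researcher who photographs the meal and very probably knows the condition; masking is not stated, and the 10% check addresses reliability only. Bias is possible, not shown.

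Its size cannot be computed from the documents. The illustrative d values depend on the assumed salt content, SD and shift, and on the shift applying to every plate in one arm. A reader might take one of them, such as d = 0.10 against the design value of 0.35, as an estimate of the bias. It is not: each of its inputs is assumed, and small shifts or many cleared plates would bring the effect close to nothing. Nor does the weakness extend to the primary PME result, to the choice outcomes taken from the order or to the interim decision.

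**What to change.** Change Total salt consumed so that percentage-eaten estimates are made after the visits, from photographs under a condition-free ID and presented in random order, by a study researcher who did not attend that table. Withhold the condition key until the ratings are locked. Because a whole table shares one condition, shuffle across tables. Both menus list the same dishes, so the dish does not by itself reveal the arm.

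Three details go with this:
- The rater needs the food-sharing answers, which sit in the same Appendix E questionnaire as the A/B letter. Supply them in an export without that letter.
- Confirm that the photographs show neither menu nor sticker.
- Do the 10% double rating under the same masking.

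The cost is some coordination, and the existing second researcher may rate more than 10% of meals. If every researcher attended a given table, rate its recoded, shuffled photographs after a delay and report the masking as partial. No new outcome data are needed, and sample size and alpha are unchanged.

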To date, the impact of nutrient warning labels has not been tested in a real-world randomised controlled trial (i.e., in a restaurant), or in a UK context. Recent work suggests that UK consumers support the introduction of nutrient warning labels, and their PME was rated as significantly higher relative to a control label (QR code) (13). This study aims to test the effect of a menu featuring salt warning labels (design informed by previous work (13)) on perceived message effectiveness relative to a menu with no labels in a real-world restaurant environment. The study will also act as a pilot experiment for examining the impact of the salt warning label on food choice and subsequent salt intake in real-world conditions.

Primary objectives:

- To measure the PME of a menu featuring salt warning labels relative to a menu with no labels
- To measure label awareness, perceived knowledge gain, and perceived influence of the label on food choice

Secondary objectives:

- To identify whether there is an effect of the salt warning label on:
 - Food choice (label/no label)
 - Total salt selected
 - Total salt intake
- To examine support for the introduction of a salt warning label policy in the UK

Experimental design

The study will be a between-subjects randomised controlled trial design. The between-subject factor is the menu labelling. In the experimental condition, a nutrient warning label will be placed next to menu items that are high in salt. In the control condition, there will be no labels. The outcome will be (i) perceived message effectiveness, (ii) salt selected, label (y/n) selected, and salt intake. This will allow us to examine whether the salt warning label intervention impacts perceived message effectiveness and food choice relative to the control condition.

Participants and recruitment

Recruitment

Participants will be recruited via social media adverts (Facebook, Instagram), a database maintained by researchers at the University of Liverpool, and word of mouth. Interested participants will be asked to click a link which will take them to an online screening questionnaire (Appendix A). Participants can bring a maximum of nine guests to the restaurant. Guests will be pre-screened in advance to ensure eligibility. In pre-study instructions participants will be informed that any guests they bring will participate in the study.

Sampling

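### How shared food enters each diner's salt intake is undefined, and food eaten from another diner's order is not recorded

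*Combined protocol and SAP*

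**What the plan says.** Under Secondary outcomes, Total salt consumed, the outcome starts from the participant's own order: "Salt consumption will be determined from the order that the researcher takes and an estimation of the proportion of the meal that was consumed". The same paragraph says "Participants will also be asked whether they shared any of their meal with someone else", which puts the question from the giver's side. Sharing then enters the calculation only through a parenthesis: "taking into account if any has been shared) from the food purchase". No direction, formula or rule for the recipient follows.

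The Procedure section words the question differently, as "whether any food or drink items were shared with other participants, and, if so, what item(s) were shared". The Food sharing block of Appendix E asks "Did you share any of the food or drink items" and, if yes, "What items were shared? Please also give an estimation in % of how much of each item was shared". Either the giver or the receiver could answer these items. Neither has a field for the other person or for food received.

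Two design features bear on this. The Recruitment section says "Participants can bring a maximum of nine guests to the restaurant" and makes those guests study participants. The Intervention section assigns everyone at a table to the same condition.

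**The concern.** Total salt intake is a named secondary objective, tested by linear regression at alpha .05. The introduction also presents the study as a pilot for measuring the label's effect on salt intake in real conditions. The sponsor expects some sharing, since it wrote questions about it.

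If one diner gives food to another at the same table, both are normally in the analysis and in the same arm. A calculation that reduces the giver's intake without raising the recipient's loses that salt from the arm. The photographs do not help: a giver's cleared plate looks fully eaten, and the recipient's plate need not show what came from elsewhere. Self-report is therefore the only planned source on sharing, and it lacks the fields needed to move salt from one diner to another. At tables of more than two this usually cannot be reconstructed after the visit.

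**Working it through.** **Benchmark from the plan.** The Sample size section gives 260 participants (130 per condition) for d = 0.35, 80% power, two-tailed. The normal approximation at alpha 0.05 gives 129 per arm. The t-test solution is 129.1, rounded up to 130 per arm, or 260. The figure reproduces, and nothing below changes it; d = 0.35 serves only as a yardstick.

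**Inputs.** From the documents: labelled dishes contain more than 3 g of salt (Intervention section), so S = 3 g is used as a round value at that threshold. Assumed, because the documents give no values: the share of the dish given away f, the sharing rates, the SD of salt intake, and the salt in the recipient's own dish.

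**One pair at a table.** A orders a 3 g dish and gives half to B, whose own order contains 1 g. Both clear their plates.

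| Handling of sharing | A | B | Table |
|---|---|---|---|
| True intake | 1.5 g | 2.5 g | 4.0 g |
| Deduct from A only | 1.5 g | 1.0 g | 2.5 g |
| No adjustment | 3.0 g | 1.0 g | 4.0 g |

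Deduction alone loses 1.5 g, and 1.5/4.0 = 37.5%. If A gives a quarter, the loss is 0.25 × 3 = 0.75 g, and 0.75/4.0 = 18.75%. A's lower figure is correct; the error is the salt missing from B. With no adjustment the table total is right and only the split between diners is wrong. A one-sided allowance can therefore be worse for the arm mean than none.

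**Equal sharing in both arms.** If a proportion q of diners in each arm give away a fraction f, and the loss is proportional to salt, both means are multiplied by (1 − q × f).
- q = 0.10, f = 0.25: 1 − 0.025 = 0.975
- q = 0.20, f = 0.50: 1 − 0.10 = 0.90

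A null difference stays null. A real one shrinks by 2.5% to 10%.

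**Unequal sharing.** If the proportion of givers is higher by p in the labelled arm, the false difference under deduction alone is p × f × S.
- Low: 0.05 × 0.25 × 3 = 0.0375 g, about 0.04 g
- Middle: 0.10 × 0.50 × 3 = 0.15 g
- High: 0.20 × 0.50 × 3 = 0.30 g

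With an assumed SD of 1 to 2 g, the extremes are d = 0.0375/2 = 0.02 and d = 0.30/1 = 0.30. The middle case is d = 0.15/2 = 0.075 to 0.15/1 = 0.15. All lie below the planned 0.35.

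**The case against.** A reader might infer that the plan takes shared food off the orderer and never credits the eater, so that sharing a labelled dish would pass for a label benefit. The documents do not support that reading.

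- **The deduction is not written down.** The plan says only that sharing will be taken into account. Neither a debit nor the absence of a credit is stated.
- **Some reconciliation is possible.** Appendix E names the item and a percentage, and the Appendix D order form lists table number, group size, study ID and each person's meal. A shared item can often be traced to its orderer, and at a two-person table the recipient is known.
- **The direction of bias is not established.** Favouring the label requires more sharing, or sharing of saltier dishes, in the labelled arm. Nothing in the documents shows either.
- **The menu gives limited support.** Half the dishes are light bites or small plates, but four of the five labelled items are mains. Ten at a table is a ceiling; no typical group size is given.
- **The reach is narrow.** PME, for which the study is powered, is untouched. Salt purchased uses the full order, so a difference in intake without one in purchase would invite scrutiny.

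All of these stand, and they limit the point. They do not remove it. However the parenthesis is read, no rule covers the recipient and no field records food received. If giver and recipient both report the same dish, nothing says whose intake is adjusted.

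**Conclusion.** The point holds as a gap in measurement and definition for one secondary outcome. The plan does not define how shared food changes a diner's recorded intake, and at tables of more than two it usually does not collect what is needed to assign that food to the person who ate it.

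The consequence depends on the rule eventually applied. Only deduction without a matching credit loses salt from the arm, and only unequal sharing then turns the loss into an apparent label effect. The size is unknown: the calculated ranges rest on assumed sharing rates, portions and SDs and are illustrations, not estimates. This is worth correcting because the repair is cheap and the missing information cannot be recovered reliably later. It does not threaten the primary outcome or the sample size.

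**What to change.** 1. Replace the sharing item in Appendix E with two questions: what the respondent gave away (item, to whom, percentage), and what the respondent ate from others' orders (item, whose order, percentage). Align the wording in the Procedure and Total salt consumed sections with it.
2. Define intake as salt eaten from the participant's own order, excluding the share given away, plus salt eaten from other people's orders. This should also replace the present subtraction wording, which read literally yields what was left on the plate.
3. For each table with sharing, check portions given against portions received using the order form, and count each shared portion once.
4. As an optional sensitivity analysis, compare table totals with no deduction for food passed between diners at the same table. These totals do not depend on who ate the shared portion.

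The cost is one extra questionnaire item and a short reconciliation for each table that shares. No additional participants, staff or visits are needed.
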